4. Whether it constitutes a SAE (see [Section 10.1.3](#) for definition of SAE) and which seriousness criteria have been met.
5. Action taken regarding investigational treatment and other treatment.

All AEs must be treated appropriately. Treatment may include one or more of the following:

- Dose not changed

- Dose reduced/increased
- Drug interrupted/withdrawn.

6. Its outcome (not recovered/not resolved; recovered/resolved; recovering/resolving, recovered/resolved with sequelae; fatal; or unknown).

Conditions that were already present at the time of informed consent should be recorded in the patient's medical history.

Adverse events (including laboratory abnormalities that constitute AEs) should be described using a diagnosis whenever possible, rather than individual underlying signs and symptoms.

Adverse event monitoring should be continued for at least 20 weeks (or 5 half-lives or end of study visit, whichever is longer) following the last dose of study treatment.

Once an AE is detected, it must be followed until its resolution or until it is judged to be permanent (e.g. continuing at the end of the study), and assessment should be made at each visit (or more frequently, if necessary) of any changes in severity, the suspected relationship to the investigational drug, the interventions required to treat it, and the outcome.

Information about common side effects already known about the investigational drug can be found in the IB. This information will be included in the patient informed consent and should be discussed with the patient during the study as needed. Any new information regarding the safety profile of the medicinal product that is identified between IB updates will be communicated as appropriate, for example, via an IN or an aggregate safety finding. New information might require an update to the informed consent and has then to be discussed with the patient.

Abnormal laboratory values or test results constitute AEs only if they fulfill at least one of the following criteria:

- they induce clinical signs or symptoms
- they are considered clinically significant
- they require therapy

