12.5.2 Analysis of secondary safety endpoints

For all safety analyses, the Safety Set will be used. All listings and tables will be presented by treatment group.

Safety summaries (tables, figures) will include only data from the on-treatment period with the exception of Baseline data, which will also be summarized where appropriate (e.g. change from Baseline summaries). In addition, a separate summary for death including on-treatment and post-treatment deaths will be provided. In particular, summary tables for AEs will summarize only on-treatment events, with a start date during the on-treatment period (i.e. treatment-emergent AEs as defined below).

The on-treatment period lasts from the date of first administration of study treatment to 30 days after the date of the last actual administration of any study treatment.

Adverse events

All information obtained on AEs will be displayed by treatment group and patient.

The number (and percentage) of patients with treatment-emergent AEs (defined as events started after the first dose of study medication or events present prior to start of study treatment but increased in severity based on PT) will be summarized in the following ways:

- By treatment, primary system organ class and PT.
- By treatment, primary system organ class, PT and maximum severity.
- By treatment, standardized MedDRA query and PT.

Separate summaries will be provided for study medication related AEs, death, SAEs, other significant AEs leading to discontinuation, AEs leading to dose adjustment and AE of special interest.

Adverse events will be summarized by presenting, for each treatment group, the number and percentage of patients having any AE, having an AE in each primary system organ class and having each individual AE (PT). Summaries will also be presented for AEs by severity and for study treatment related AEs. If a patient reported more than one AE with the same PT, the AE with the greatest severity will be presented. If a patient reported more than one AE within the same primary system organ class, the patient will be counted only once with the greatest severity at the system organ class level, where applicable. Serious adverse events will also be summarized.

Vital signs

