2.1.1 General definitions

Study treatment: Study treatment refers to:

1. Investigational treatment Treat to Target (T2T) = secukinumab 150 mg and/or 300 mg and/or adalimumab biosimilar 40 mg (GP2017)
2. Standard of Care (SOC) treatment up to the maximum recommended dose at the discretion of the investigator

The **treatment phase** is defined as the period from randomization until end of the last treatment period with treatment periods defined as:

- Period 1: date of randomization until day before visit Week 12
- Period 2: date of visit Week 12 until day before visit Week 24

- Period 3: date of visit Week 24 until day before visit Week 36

The following exceptions are made to these definitions:

- If visit Week 12 or 24 is missing but the next visit is documented, the visit date is interpolated in the middle between the earlier and the later visit.
- End dates of period 1, 2, 3: If no further visit was performed during the treatment phase after start of the period, the end date is set to the documented end of treatment date or to the period start date, if no treatment was applied in this period.
- End date of period 3: If the documented end of treatment date is on visit Week 36 date or later, the end date of period 3 is set to the end of treatment date.
- Treat-to-Target group: If treatment was not applied at visit Week 12 or 24, or the last dose of the previous period was still applied on the date of visit, the start date of period 2 resp. 3 is set to the date of first dose in this period. Cases where the last dose of the previous period was still applied on the visit date are identified by the same dose as in the previous period applied on the visit date, but treatment was switched at the first dose after the visit.

Treat-to-Target regimen

Starting from Baseline, subject will be treated with secukinumab 150 mg subcutaneous (s.c.) weekly until Week 4 and then at Week 8.

At Week 12

- If the subject achieves and maintains an ASDAS clinically important improvement (i.e. change from Baseline in ASDAS ≥ 1.1 indicating subjects is a responder), then the subject will continue with secukinumab 150 mg s.c. every 4 weeks up to Week 32.
- If the subject did not achieve ASDAS clinically important improvement (i.e. non-responder) then the subject will receive an escalated dose of secukinumab 300 mg s.c. every 4 weeks until Week 20.

At Week 24

Subjects who are receiving secukinumab 300 mg and

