- Achieves ASDAS clinically important improvement (i.e. responder) will continue with secukinumab 300 mg s.c. every 4 weeks up to Week 32.
- Do not achieve ASDAS clinically important improvement (i.e. non-responder), will be switched to adalimumab biosimilar (GP2017) 40 mg s.c. every 2 weeks until Week 34.

Escape arm

- Subjects who are receiving 150 mg secukinumab (i.e. were responders at Week 12) can be escalated at Week 24 to 300 mg secukinumab every 4 weeks until Week 32 if they experience a loss of response, where loss of response is defined as ASDAS change from Baseline <1.1 .

If the ASDAS measurement is missing at a visit, it is assumed that the planned dose continues for the next treatment period.

Standard of Care Regimen

Patients will receive treatment according to local practice standards by their treating physician following the current treatment recommendations with NSAIDs as the first-choice drug treatment and disease-modifying anti-rheumatic drugs (DMARDs) for patients with active disease because of a lack of response, intolerance, or contraindication to NSAIDs ([van der Heijde et al 2017](#)). Patients will be seen every 12 weeks or more often, if clinically indicated up to Week 36; assessment of the outcome parameters will be performed at Week 12, Week 24 and Week 36.

Study treatment (T2T) start and end date: Study treatment start date is defined as the first date of study drug administration and recorded on the Drug Administration Record (DAR) Electronic Case Report Form (eCRF) page. Similarly, study drug end date is defined as the last date of study drug administration and is recorded on the DAR eCRF page.

SOC treatment start and end date: SOC treatment start date is defined as the first date of any SOC drug for AxSPA treatment after randomization. Similarly, SOC drug end date is inferred as the last date of any SOC drug administration for AxSPA treatment within the treatment phase.

Study day: Study Day 1 is defined as the first day of administration of randomized study treatment. Study day will be calculated as (event date – study drug start date + 1 day) for events that occurred on or after study drug start date (e.g. visit, lab samples, AEs). For events prior to study drug start date (e.g. time since diagnosis), study day will be negative and calculated as (event date – study drug start date).

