Baseline and post-Baseline: Baseline value refers to the value of the last non-missing measurement collected prior to administration of the first dose of study treatment (screening or Baseline visit). A post-Baseline value refers to a measurement taken after the first dose of study treatment.

Change from Baseline: The difference of measure between post-Baseline and Baseline is called change from Baseline.

Percent change from Baseline: The percent change from Baseline will be calculated as below:
 $((\text{post-Baseline value} - \text{Baseline value}) / \text{Baseline value}) * 100$.

On-treatment period: The on-treatment period lasts from the date of first administration of study treatment to 30 days after the date of the last actual administration of any study treatment or end of treatment phase, whichever is later.

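### AE and SAE summary tables stop at an on-treatment window that leaves out 79% to 99% of the post-Week 36 follow-up, and whose ambiguous, undeclared end rule can give the arms different lengths

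*SAP*

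**What the plan says.** **Collection.** Protocol 10.1.1: "Adverse event monitoring should be continued for at least 20 weeks" after the last dose (longer if 5 half-lives or the end-of-study visit comes later). Protocol 3 and SAP 1.1 place the safety follow-up visit at Week 56, 20 weeks after Week 36.

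**Tabulation.** Protocol 12.5.2 and SAP 2.8.1 both limit AE summary tables to events that start in the on-treatment period, reported as numbers and percentages of patients. Two outputs go further. SAP 2.8.2 summarizes post-treatment deaths, and SAP 2.8.1 lists all treatment-emergent AEs, whose definition carries no end date.

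**End of the window, protocol.** Protocol 12.5.2: "The on-treatment period lasts from the date of first administration of study treatment to 30 days after the date of the last actual administration". The rule applies to every study drug and has no other limb.

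**End of the window, SAP.** SAP 2.1.1 repeats this and adds a limb, so that the sentence closes with "or end of treatment phase, whichever is later". The treatment phase is visit-based and defined for both arms: "Period 3: date of visit Week 24 until day before visit Week 36". If the documented end of treatment falls on or after the Week 36 visit, "the end date of period 3 is set to the end of treatment date".

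**Last dose.** Protocol 6.1.3 puts the last secukinumab dose at Week 32 and the last adalimumab dose at Week 34. For SOC, SAP 2.1.1 says: "SOC drug end date is inferred as the last date of any SOC drug administration for AxSPA treatment within the treatment phase".

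**Declaration.** SAP Section 4 records no change to the protocol-specified analyses.

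**The concern.** The secondary safety endpoint is the number and percentage of patients with treatment-emergent AEs. The 20-week follow-up exists to catch late events, and the protocol treats the period after the last dose as relevant well beyond 30 days. Its contraception requirement cites 20 weeks for secukinumab and 5 months for adalimumab, and Protocol 6.5 says adalimumab elimination may take up to 4 months. If the tables stop about when the follow-up begins, a late infection or other SAE appears only as a line in a listing, with no count or percentage by arm.

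A second issue is comparability. T2T drugs are injected at intervals and stop at Week 32 or 34, while an SOC patient may take an NSAID daily up to Week 36. A window anchored on the last dose can then be longer in SOC, and crude percentages do not absorb the difference.

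Third, the SAP sentence can be programmed in two ways and differs from the protocol without being declared.

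**Working it through.** **Day convention.** Nominal day = 7 × week + 1. Week 36 gives 7 × 36 + 1 = Day 253, the scheduled day in SAP Table 2-1. Week 56 gives Day 393. Follow-up after the Week 36 visit is 393 − 253 = 140 days, which is the stated 20 weeks.

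**Inputs.** Secukinumab last dose: Week 32, Day 225. Adalimumab last dose: Week 34, Day 239. End of treatment phase: day before the Week 36 visit, Day 252. SOC last dose: Day 252 for a drug taken daily to the end of the phase (assumption); Week 34 or Week 32 as illustrations of interval-dosed drugs (assumption).

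**Two readings of the SAP sentence.**

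- Reading 1: window end = max(last dose + 30, end of phase).
- Reading 2: window end = max(last dose, end of phase) + 30.

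The protocol rule is last dose + 30. For the completers below it gives the same day as reading 1.

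| Completer | Last dose | End, reading 1 | Follow-up days inside (end − 253) | Outside, of 140 |
|---|---|---|---|---|
| Secukinumab | Day 225 | 255 | 2 | 138 (98.6%) |
| Adalimumab | Day 239 | 269 | 16 | 124 (88.6%) |
| SOC, daily drug | Day 252 | 282 | 29 | 111 (79.3%) |
| SOC, last drug at Week 34 | Day 239 | 269 | 16 | 124 (88.6%) |
| SOC, last drug at Week 32 | Day 225 | 255 | 2 | 138 (98.6%) |

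Under reading 2 every row ends at 252 + 30 = Day 282, with 29 days inside and 111 of 140 (79.3%) outside.

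**Gap between arms, reading 1.**

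- Daily SOC against secukinumab: 282 − 255 = 27 days (3.9 weeks).
- Daily SOC against adalimumab: 282 − 269 = 13 days (1.9 weeks).
- SOC last given at Week 34 against secukinumab: 269 − 255 = 14 days.
- SOC last given at Week 32 against secukinumab: 0 days.

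Under reading 2 all these gaps are 0.

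**Effect of the added limb.** Take a T2T patient whose last dose is at Week 8 (Day 57) and who keeps attending visits. The protocol window ends on Day 57 + 30 = Day 87. The SAP window ends on Day 252 (reading 1) or Day 282 (reading 2). The undeclared change therefore alters which events are counted.

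**Which reading is meant.** SAP 2.4.1 computes on-treatment exposure as last dose − first dose + 1 + 30, and SAP 2.8.3 treats laboratory data more than 30 days after the last dose as post-treatment. Both attach the 30 days to the last dose, which favours reading 1. They also mean that AEs, exposure and laboratory data can follow different windows in the same patient.

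**The case against.** The strongest reply is that restricting summaries to on-treatment data was prespecified in the protocol and that no between-arm test of AEs is planned. The objective is the overall safety and tolerability of secukinumab, so any effect is on descriptive tables. That is right, and it limits the weight of the point. It does not remove it, because those percentages are the reported safety result.

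The added limb also does some good. It brings early stoppers in both arms up to at least the end of the treatment phase. That is a reason to declare it and word it clearly.

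A reader might infer that the window is simply last dose + 30 days, so that SOC always gets about 4 weeks more and the AE comparison favours T2T by construction. The documents do not support this:

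- The SAP sentence has a second limb, and on reading 2 the gap vanishes.
- On reading 1 the 27 days apply only to secukinumab completers against SOC patients dosed up to Week 36. Protocol 6.1 provides for bDMARDs in SOC, which may be given at intervals.
- SAP 2.1.1 starts SOC treatment at the first SOC axSpA drug after randomization, and a late start shortens that arm's window.
- T2T patients have extra safety visits at Weeks 4 and 8, which could raise AE detection in T2T.

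Turning 27 days into percentage points needs an AE rate that the documents do not give, so no such figure is claimed.

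It would also be too strong to say that late events enter no output at all, given the deaths summary and the listings.

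**Conclusion.** The point holds in this form. For completers, 79% to 99% of the 140-day follow-up after Week 36 lies outside all AE and SAE summary tables under either reading. The arm difference is conditional: 0 to 27 days against secukinumab under reading 1 for SOC patients still dosed at Week 32 or later, and 0 under reading 2. Its direction in the reported percentages is not established. The SAP definition departs from Protocol 12.5.2 without a declaration in Section 4, and it is open to two programs.

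Assumptions: nominal visit days, treatment completed, first dose on the day of randomization, and a daily SOC drug taken to the day before the Week 36 visit. If a documented SOC end of treatment falls on or after that visit, the period 3 exception moves the end of the phase. The SOC window could then run past Day 282 and the gap exceed 27 days.

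This is a cheap improvement to descriptive safety reporting. It does not affect the primary efficacy analysis.

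**What to change.** 1. Keep the on-treatment table, but write its end as one formula in SAP 2.1.1: either the later of (last dose + 30 days) and the end of the treatment phase, or 30 days after the later of last dose and end of phase. State whether exposure (2.4.1) and laboratory data (2.8.3) follow the same rule.
2. Add AE and SAE summaries over a common calendar window for both arms: randomization to the Week 36 visit, and randomization to Week 56. Starting at randomization avoids the variable SOC start date. Keeping the on-treatment table means that adalimumab events in the 16 days after the Week 36 visit (Day 254 to Day 269) are not lost.
3. Record the changed on-treatment definition in SAP Section 4.

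The cost is one more set of tables; no new data are needed. One limitation should be printed on the Week 56 table: after Week 36 the T2T study drug has ended while SOC therapy may continue, so the table does not compare two arms under ongoing treatment.

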2.1.2 Visit windows for data analysis

Visit windows will be used for data analyses which are summarized by visit. This is based on scheduled visits and comprises a set of days around the nominal visit day. Randomization of subjects will take place at Baseline; subjects will have a maximum of 14 scheduled post-Baseline assessments and 1 follow-up assessment after 20 weeks. The data will be analyzed at Baseline, Week 12, Week 24 and Week 36. A follow-up visit will take place at Week 56.

In case of more than one post-Baseline assessment due to unscheduled visits, the assessment closest to the scheduled post-Baseline day will be used for analysis. For the summary of notable

laboratory abnormalities, the most extreme post-Baseline measurement will be used for analysis in case of more than one post-Baseline assessment. In the event two measurements are taken equally apart (e.g., 1 day before target date and 1 day after), the earlier one will be used.

Table 2-1 Assessment windows for scheduled visits

Analysis Visit	Week	Scheduled Day	Visit Window
Baseline	BSL	1	-28 days to Day 1*
Week 12	12	85	Day 2-Day 127
Week 24	24	169	Day 128-Day 211
Week 36	36	253	Day 212-Day 364

* Baseline measurement before the first drug administration.

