ASAS=Ankylosing SpondyloArthritis International Society, ASDAS=AS disease activity score, ASQoL=ankylosing spondylitis quality of life, BASDAI=Bath ankylosing spondylitis disease activity index, BASFI=Bath ankylosing spondylitis functional index, BASMI=Bath ankylosing spondylitis Metrology Index, CRP=C-reactive protein, ESR=erythrocyte sedimentation rate, FACIT-Fatigue=functional assessment of chronic illness therapy – fatigue, [REDACTED] MRI=magnetic resonance imaging, PR= partial remission, SF-36=Short form health survey, SOC=standard-of-care, VAS=visual analog scale

3 Study design

This is a randomized, parallel-group, open-label, multicenter study in patients with active axSpA. The aim of the study is to demonstrate that the efficacy of a T2T approach (with secukinumab as a first-line biologic) is superior to a SOC approach in terms of achieving strong clinical efficacy in patients with active axSpA who are naïve to biological therapy and who have an inadequate response to prior NSAID treatment. The study will include an 8-week Screening period, a 36-week treatment period, and a 20-week safety follow-up period. Neither investigators nor patients will be blinded. The primary endpoint is the percentage of patients achieving an ASAS40 response at Week 24. At Baseline, patients will be randomized equally to one of 2 treatment groups (T2T or SOC) as shown in [Figure 3-1](#):

Figure 3-1 Study design

Patients will be evaluated every 12 weeks from Baseline up to Week 36. Safety evaluations will be included in the regular visits; in addition, a safety follow-up visit will be performed 20 weeks after the last study visit (i.e. Week 36) and will take place at Week 56 for patients completing the study according to the protocol. In addition, patients in the T2T arm will be seen for safety monitoring at Visit 4 (Week 4) and Visit 5 (Week 8). Patients who prematurely discontinue completely from the study for any reason should return for the final visit to conduct the Week 36 assessments (4 weeks after the last study treatment administration), then also return after an additional 20 weeks for a final follow-up visit, corresponding to Week 56 assessments.

T2T group (n = 150)

Starting from Baseline, patients will be treated with secukinumab 150 mg subcutaneous (s.c.) weekly until Week 4 and then at Week 8.

At Week 12:

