Neutropenia was more frequently observed with secukinumab than with placebo, but most cases were mild, transient, and spontaneously reversible.

The incidence of hypersensitivity AEs was slightly higher with secukinumab compared with placebo, with the difference mostly due to mild to moderate urticaria and eczema not associated with systemic symptoms.

The incidence of selected rare events of interest (major adverse cardiovascular events and malignancies) adjusted for exposure over 52 weeks was comparable to placebo in clinical trials across multiple indications.

There was no clear association between treatment with secukinumab and new onset of inflammatory bowel disease but due to the potential involvement of the interleukin-17 (IL-17) pathway in the pathogenesis of the disease, it is not possible to rule out a potential increased risk of exacerbation.

Secukinumab 300 mg was comparable to 150 mg and both doses showed comparable safety to placebo and etanercept over 52 weeks of treatment.

Infections, neutropenia, and hypersensitivity are important identified risks, while malignancies, major adverse cardiovascular events, immunogenicity, Crohn's disease, and hepatitis B reactivation are important potential risks. Interaction with live vaccines is an important potential interaction (and also included as an important potential risk).

No new identified risks were reported. During the reporting interval, a Risk Management Plan (RMP) update was triggered upon request from Pharmacovigilance Risk Assessment Committee, to include suicidal ideation and behavior (SIB) as an important potential risk in the RMP on the basis that "although causality has not been established, SIB meets the criteria as important potential risk because a potential biological mechanism cannot be completely ruled out since the biological role of IL-17 receptor ligands is still largely unknown, and consideration of the potential public health impact". The RMP is currently being updated for this change. At its completion SIB will be listed as an important potential risk in the RMP.

No new safety signal was identified and no actions were taken for safety reasons during the reporting period of the latest drug safety update report.

The risk to patients in this trial will be minimized by compliance with the eligibility criteria, close clinical monitoring, and extensive guidance to the investigators, provided in the current version of the Investigator's Brochure (IB).

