'S' designates assessments which are recorded in source documentation only.

'C' designates centrally analyzed laboratory or questionnaire results which are entered into the database by a central laboratory or by data management; for these assessments, only the date of the assessment needs to be entered into the eCRF by the site staff.

^a only in case the patient has been seen for the optional visit at site, else, the information will be obtained at the next obligatory site visit.

¹ As according to the DGRh recommendation, for patients treated with secukinumab following laboratory parameters should be evaluated at the therapy week 4 and 8:m ESR, hsCRP, full blood count, ALT, Creatinine.

² Eligibility and relevant medical history assessments are conducted at SV1, SV2 and Baseline but recorded only once in the eCRF.

³ The last available X-ray and/or MRI of the sacroiliac joints done in order to confirm/revise the axSpA diagnosis should be uploaded into the central reading platform.

⁴ If patients do not have a chest X-ray available within 3 months of Screening, an X-ray should be performed after it is certain the patient meets inclusion/exclusion criteria in order to minimize unnecessary exposure to X-ray radiation. In some sites selected by Novartis, the X-ray assessment may be replaced by chest MRI assessment.

⁵ MRIs performed up to 3 months prior to Screening will be accepted; MRI should be performed during Screening only if patient's quick CRP test is negative (i.e. ≤ 5 mg/L).

⁶ In case an actual (not older than 3 months) MRI image of sacroiliac joints (and spine) is available, it should be uploaded into the central reading platform. If a patient has a negative quick CRP (i.e. ≤ 5 mg/L) at Screening, a MRI of the sacroiliac joints and spine must be performed during the Screening to ensure the presence of objective signs of inflammation of the sacroiliac joint and the MRI should be uploaded into the central reading platform.

⁷ In case the patient has been already tested for HLA-B27 antigen, the result of the test will be entered in the eCRF and no central re-test will be performed.

⁹ All questionnaires will be completed at the scheduled study visit prior to the patient seeing the investigator for any clinical assessment or evaluation.

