2.8.3 Laboratory data

All laboratory data will be listed with abnormal values flagged.

Laboratory data measured more than 30 days after the last dose of study drug is regarded as post-treatment and will not be summarized or analyzed, only listed.

The below laboratory parameter data will be analyzed.

Hematology: Hemoglobin, hematocrit, platelet count, red blood cell, WBC and differential WBC counts.

Clinical chemistry: glucose, urea, creatinine, total bilirubin, AST, ALT, gamma-glutamyl transferase (GGT), alkaline phosphatase, sodium, potassium, bicarbonate, calcium, phosphorous, total protein, albumin, and uric acid.

Lipid panel: High density lipoprotein, low density lipoprotein, cholesterol and triglycerides must be measured from a fasting blood sample.

Urinalysis: Protein, glucose, blood and WBCs.

For all continuous laboratory parameters, summary statistics for absolute and change from Baseline values will be provided at each visit. All laboratory data (including any unscheduled assessments) will be listed with abnormal values flagged.

For categorical urinalysis laboratory parameters (Glucose, Occult Blood, Protein), a frequency table of results will be produced by laboratory parameter, scheduled visit and treatment.

Shift tables for laboratory parameters will be provided in order to compare a subject's Baseline value to the value at each study visit, relative to the normal reference range for each lab parameter. Abnormal values marked in Section 5.4 will be used to evaluate whether a particular laboratory test value for each visit is normal, low or high relative to the Baseline value also categorized as normal, low or high. These summaries will be presented by laboratory parameter, visit and treatment group.

In addition, shift tables relative to the normal reference ranges will be used to summarize the change from Baseline to the most extreme post-Baseline for each laboratory parameter. For each laboratory test, the subjects will be classified into one of the four mutually exclusive groups (low, normal, high, and low + high), defined as follows:

- Low: at least one post-Baseline value below the normal range and none above the normal range
- High: at least one post-Baseline value above the normal range and none below the normal range
- Normal: all the post-Baseline values within the normal range
- Low + High: at least one post-Baseline value below the normal range and at least one above the normal range

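### SAP Table 2-1 gives the T2T-only Week 4 and Week 8 laboratory draws no analysis visit and folds them into Week 12, while SAP 2.8.3 promises laboratory tables for each visit

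*SAP*

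**What the plan says.** **The draws.** Protocol Section 3 has T2T patients attend at Visit 4 (Week 4) and Visit 5 (Week 8) for safety monitoring. Footnote 1 to Protocol Table 8-1 gives the content for patients on secukinumab: "following laboratory parameters should be evaluated at the therapy week 4 and 8:m ESR, hsCRP, full blood count, ALT, Creatinine". Protocol 4.1.1 names these samples as the one difference in assessments between the arms, so SOC patients do not have them.

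**The known risk.** Protocol 4.4 lists neutropenia among the important identified risks and adds: "Neutropenia was more frequently observed with secukinumab than with placebo, but most cases were mild, transient, and spontaneously reversible".

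**The windows.** SAP 2.1.2 opens: "Visit windows will be used for data analyses which are summarized by visit". It then says: "The data will be analyzed at Baseline, Week 12, Week 24 and Week 36". Table 2-1 assigns Day 2-127 to Week 12 (target Day 85), Day 128-211 to Week 24 and Day 212-364 to Week 36. There is no separate laboratory window.

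**The selection rule.** The trigger is "In case of more than one post-Baseline assessment due to unscheduled visits", and the consequence is that "the assessment closest to the scheduled post-Baseline day will be used for analysis". Ties go to the earlier value.

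**The tables.** SAP 2.8.3 says: "For all continuous laboratory parameters, summary statistics for absolute and change from Baseline values will be provided at each visit". It also plans shift tables from Baseline to every study visit, presented by visit and treatment group.

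**The concern.** SAP 2.1.2 and 2.8.3 cannot both be followed. Section 2.8.3 promises output for every visit. Section 2.1.2 governs all by-visit output and has no Week 4 or Week 8. A programmer must choose, and each available choice treats the early T2T samples badly: they are dropped, pooled with Week 12, or sometimes labelled as Week 12.

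At stake is the time course of laboratory safety in one arm. A blood count change that is present at Week 4 or 8 and gone by Week 12 is what these draws can show and a Week 12 draw cannot. The by-visit tables would not show it at its own visit.

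The gap also reaches efficacy. ESR and hsCRP are taken at the same two visits, and change from Baseline in CRP and ESR is a secondary endpoint analysed by MMRM with visit as a factor (SAP Table 2-2). That model needs one value per patient and visit, and the SAP has no rule for several scheduled values in one window.

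**Working it through.** **Inputs.** Analysis targets and windows come from SAP Table 2-1, visit tolerances from Protocol 6.6.1, and the T2T arm size of 150 from Protocol Section 3.

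**1. Reproduce the plan's windows.** Target day = 7 x week + 1.
- Week 12: 7 x 12 + 1 = 85. Week 24: 169. Week 36: 253. All agree with Table 2-1.
- The limits between adjacent visits are midpoints: (85 + 169)/2 = 127 and (169 + 253)/2 = 211. Both agree.

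**2. Place the early draws.** The tolerances are 2 days for Visit 4, 3 days for Visit 5 and 7 days for Visit 6.

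| Draw | Target | Within tolerance | Table 2-1 window | Distance from Day 85 |
|---|---|---|---|---|
| Week 4 | Day 29 | Day 27-31 | Week 12 | 54-58 days |
| Week 8 | Day 57 | Day 54-60 | Week 12 | 25-31 days |
| Week 12 | Day 85 | Day 78-92 | Week 12 | 0-7 days |

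**3. If the closest-value rule is applied.** The Week 12 draw is at most 7 days from target and the nearest early draw at least 25. The Week 12 draw therefore wins in every in-tolerance combination, and both early values leave the by-visit tables.

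**4. If the rule is read as worded.** Weeks 4 and 8 are scheduled visits, so the rule does not cover them. A T2T patient can then contribute three values to the Week 12 row and a SOC patient one.

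**5. If the Week 12 sample is missing.** The Week 8 value (28 days from target) beats the Week 4 value (56 days) and is reported as Week 12. If Week 8 is missing too, the Week 4 value takes that label.

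**6. If the Week 12 sample is late.** With Week 8 on Day 57, a Week 12 draw on Day 85 + 28 = 113 ties and the earlier value is taken. From Day 114 to 127 the Week 8 value is strictly closer. At the ends of the Week 8 tolerance this switch starts at Day 85 + 25 = 110 or Day 85 + 31 = 116.

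**7. Size.** 150 patients x 2 draws = 300 scheduled draws without an analysis visit. The documents give no rate of missing Week 12 samples. If it were 2% to 10%, then 150 x 0.02 = 3 to 150 x 0.10 = 15 T2T patients could have an earlier value shown as Week 12.

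**8. Where the early values survive.** SAP 2.8.3 has a shift table to the most extreme post-Baseline value and flagged listings of all laboratory data. SAP 2.1.2 uses the most extreme value for the notable-abnormality summary. All three include Weeks 4 and 8. The two summaries carry no timing, and they draw on two more scheduled samples in T2T than in SOC.

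**The case against.** The strongest reply is that no safety information is lost. A low neutrophil count at Week 4 puts the patient in the low category of the most-extreme shift table, counts in the notable-abnormality summary if it meets the criterion, and is flagged in the listing. Clinically significant values also become adverse events (Protocol 10.1.1). SAP windows do not affect the monitoring of individual patients. The documents say that the draws follow a national society's recommendation; they do not say that the draws are meant to describe a time course. There is no SOC sample to compare with. Table shells and programming specifications are separate documents (SAP Section 1) and may settle the columns.

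Most of this stands, and it limits the point to timing and labelling. It does not remove the conflict. The SAP states a window rule for all by-visit output, that rule mishandles scheduled data in one arm, and unseen shells cannot be assumed to override it.

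A reader might go further and infer that the early values appear in no by-visit safety table, or that a fixed share of T2T draws is lost. The documents do not support that. It holds only if the closest-value rule is applied and the Week 12 draw wins. Under the other readings an early value does appear, in the wrong row. Section 2.8.3, read alone, promises the tables. A share would also need the full laboratory schedule, and those rows of Table 8-1 are not in the public text.

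**Conclusion.** The point holds as an unresolved conflict between SAP 2.1.2 and 2.8.3, with a selection rule that does not cover the case. It concerns two scheduled draws in each of about 150 T2T patients and none in SOC. What is lost is mainly the timing of the values and their correct visit label.

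A reader might infer that a transient neutrophil fall would go unreported. It would not: the worst-value summaries and listings still carry it.

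The conclusion rests on three readings. First, the windows of 2.1.2 apply to laboratory tables, as their opening sentence says. Second, full blood count includes neutrophils, which the footnote does not state but Protocol 8.4.4.1 suggests by listing differential white cell counts at scheduled visits. Third, the Week 4 sample precedes that day's injection, as Protocol 6.7.2 requires, so it follows four doses (Baseline and Weeks 1, 2 and 3). The primary ASAS40 analysis at Week 24 is not affected.

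**What to change.** In SAP 2.1.2, add laboratory analysis visits for T2T by the plan's own midpoint rule, (29 + 57)/2 = 43 and (57 + 85)/2 = 71:

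- Week 4: Day 2-43, target Day 29.
- Week 8: Day 44-71, target Day 57.
- Laboratory Week 12: Day 72-127, target Day 85. Week 24 and Week 36 do not change.

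All in-tolerance draws in the table above then fall in their own window.

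Produce the 2.8.3 by-visit summaries and shift tables for blood count, ALT and creatinine at the two added visits, marked as not scheduled in SOC. Extend the selection rule to scheduled duplicates, including hsCRP and ESR, so that a Week 4 or Week 8 value is never used as Week 12. Footnote the worst-value summaries to say that T2T has two more scheduled samples than SOC.

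The cost is SAP wording and two T2T-only columns in existing tables, from data already collected. No visit, dose or clinical rule changes. The small downside is that these two visits have no SOC comparison.
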